**1. PROJECT TITLE**

Precision Approach to PPI Therapy in Gastroesophageal reflux disease.

**3. FACILITIES**

University of California San Diego

**4. ESTIMATED DURATION OF THE STUDY**

5 years.

**5. LAY LANGUAGE SUMMARY OR SYNOPSIS (no more than one paragraph)**

The clinical and financial burden of patients with suspected reflux associated laryngeal symptoms (RALS) is substantial. RALS is the process where gastro-esophago-pharyngeal reflux contributes to chronic laryngeal symptoms such as sore throat and dysphonia. The objectives of this proposal are to understand the performance of standard of care diagnostic tools and treatment options among suspected RALS.

**6. SPECIFIC AIMS**

**Aim 1:** To determine the ability of novel diagnostic tools to predict symptom-based treatment response in suspected RALS.

Hypothesis: Salivary pepsin will have high sensitivity for response to proton pump inhibitor (PPI); pH-impedance (Z2pH) and esophageal manometry (HRIM) will have high specificity for response to Upper esophageal sphincter assist device (UESAD) in adjunct to PPI.

**Aim 2:** To examine the therapeutic efficacy of UES augmentation in suspected RALS.

Hypothesis: UESAD in adjunct to PPI will result in greater symptom response versus PPI alone.

Approach: We will perform an 8 week clinical trial. Patients with suspected RALS will undergo baseline standard of care diagnostic tests (esophageal manometry (HRIM), pH-impedance (Z2pH)) and research diagnostic test (salivary pepsin) followed by two standard of care therapies (PPI x 4 weeks followed by UESAD in adjunct to PPI x 4 weeks).

**7. BACKGROUND AND SIGNIFICANCE**

Reflux associated laryngeal symptoms (RALS), coined "laryngopharyngeal reflux", occurs when gastro-esophago-pharyngeal reflux contributes to chronic laryngeal symptoms such as throat clearing, sore throat and dysphonia. Over the past 25 years, RALS has been increasingly, and often incorrectly, diagnosed and has emerged as a point of controversy and confusion.

**Critical Healthcare Burden RALS is prevalent, costly, and impairs quality of life** Fifty percent of

patients with laryngeal symptoms are considered to have RALS, although 60% of cases are likely misdiagnosed. The evaluation of suspected RALS entails an average of 10 specialist office visits and 6 diagnostic tests, often without clarity or improved health-related quality of life. This redundant and ineffective clinical paradigm contributes to health care costs of \$5,438 per patient, equating to over \$50 billion annually. Thus, there is a critical need for cost-effective and patient-centered approaches to suspected RALS.

### **Clinical Barrier Treatment strategies for suspected RALS are inappropriately generalized**

Patients presenting with laryngeal complaints are heterogeneous in terms of symptom presentation, underlying physiology, and response to treatment. For instance, non-reflux mechanisms commonly generate laryngeal irritation; in these cases acid suppression and anti-reflux therapy is unwarranted. Nonetheless, the majority of patients with suspected RALS are trialed on empiric PPIs over long and oftentimes indefinite intervals. However, fewer than 50% of patients will derive symptom relief with PPI therapy. The low response to PPI therapy relates to the dilutional effect of patients incorrectly considered to have RALS. Furthermore, anti-reflux surgery is often considered, even though anti-reflux surgery is invasive, morbid and costly, and not shown to improve outcomes. Thus, effective, safe, and personalized treatment options are needed.

### **Diagnostic Challenges Current diagnostic tools are unable to reliably identify RALS**

A major barrier to identifying true RALS is that traditional diagnostic tools assess anatomic or physiologic properties in isolation, resulting in poor specificity, sensitivity, and prognostic ability

#### **8. PROGRESS REPORT**

Start Date: July 1, 2018 (University of Colorado)

Total enrolled: 17.

Total completed phase 1 (PPI trial): 15

Total completed phase 1 and 2 (PPI trial & UESAD): 8

Currently enrolled: 2

Dropped out or lost to follow-up: 1

#### **9. RESEARCH DESIGN AND METHODS**

**Study Design:** This is a prospective multicenter single-arm non-randomized non-controlled clinical trial registered with clinicaltrials.gov. This study will be performed at the UCSD Medical Campus and the University of Colorado (CU) Medical Campus. With regards to IRB the plan is that University of Colorado will have IRB oversight of the study activities at University of Colorado and UCSD will have IRB oversight of study activities at UCSD. The study has already been active and IRB approved at University of Colorado. (IRB Approval letter from University of Colorado included)

**Setting at UCSD:** Patients will be enrolled from clinics of study investigators that are also the treating provider for the patient. Therefore, the patients are known to the investigator and have a treatment relationship. Inclusion and exclusion criteria are below. The clinics are clinics of [name], [name], [name], [name], [name].

#### **Study Protocol:**

**Screening:** Upcoming clinics staffed by study investigators will be screened by Research Assistant (RA) to identify potential participants. The PI/RA will notify the study investigator MD of patient's eligibility. Once investigator approves, the RA will contact the potential research participant by phone to provide information about the study, determine eligibility, and answer any questions.

**Standard of care Clinic Visit (Visit 1):** At the already scheduled standard of care clinic visit the treating physician will provide the potential participant with information regarding the study. If the patient is interested in participating in the study, the RA will review the study in detail and obtain informed consent. At this time requests for procedures, office visits, and PPI therapy will be placed to the insurance company during this standard of care visit so that the participant understands expense coverage at the onset of study participation.

Saliva samples will be collected non-invasively via the method described below and analyzed for pepsin concentration. Saliva sample collection will be performed in the motility lab and will add two minutes to the visit time. Salivary peptest is FDA approved though not a SOC procedure at UCSD and therefore the supplies will be covered through research costs and analyses will be performed by the research team. There are no expected costs to manage side effects.

**Standard of Care Drop off of Ph Impedance Catheter (Visit 3):** Participants will return the pH impedance catheter to the motility lab as per SOC. There are no costs associated with this visit.

**PPI Therapy (Weeks 0 to 4):** Following the diagnostic evaluation (visit 2 & 3) the participants will start their 4 week course of PPI therapy. PPI therapy is an FDA approved standard treatment per national guidelines and recommendations, and is the SOC practice at UCSD covered by insurance. The 4 week course of PPI therapy is not an intervention. Per SOC the PPI will be Omeprazole 40mg BID or equivalent; 4 weeks is chosen given reports of esophagitis healing within 2 weeks of PPI. The PPI will be obtained through the participant's pharmacy. The RA will call the participant at week 2 and week 3 of PPI therapy per phone script attached to review appropriate PPI use, adherence, and remind the participant of the mid-treatment visit.

**Mid-Treatment Visit (Visit 4):** After 4 weeks of PPI therapy, the participant will present to a clinic room at Clinical Trial Research Institute for a mid-treatment visit. During this visit the PI/RA will collect a saliva sample non-invasively via the method described below and analyzed for pepsin concentration (2 minutes). The participant will complete a SOC questionnaire to assess clinical outcomes following the PPI therapy. The participant will be given an UES assist device. The PI/RA will fit the UES assist device during this visit and educate the participant on use of the UES assist device. The UES assist device is an FDA approved non-invasive device that is available over the counter for this proposed participant population, and is not considered a research intervention. For this study the research team will provide the UES assist device free of cost to the participant. Therefore, the participant will not incur any costs related to the UES assist device. The visit duration will be 30 minutes.

**UES Assist Device & PPI Therapy (Weeks 5 to 8):** The participant will use the UES assist device and continue their PPI therapy for 4 weeks. The RA will call the participant at week 5 and 7 therapy per phone script attached to review appropriate use, adherence, and remind the participant of the mid-treatment visit.

**Post-Treatment Clinic Visit (Visit 5):** Participants will return to the treating MD's clinic at the end of the 8 week treatment to review test results, symptom response, and discuss next steps as per standard of care. For patients without signs of esophagopharyngeal reflux or GERD, MD will recommend further evaluation by either laryngology, asthma, allergy, and/or behavioral psychology as indicated by standard practice. During this visit, the PI/RA will collect a saliva sample non-invasively via the method described below and analyzed for pepsin concentration (2 minutes). The participant will complete a SOC questionnaire to assess clinical outcomes following the PPI + UES assist device therapy. Participants are permitted to keep the UES assist device if they intend to continue to use it, free of cost.

**Phone Call:** The PI/RA will call the participant at week 20 with basic questions about their progress after the completion of the trial, whether they have continued using the reflux band, and their current

medications to understand long-term outcomes and adherence.

Typically, patients with suspected RALS will see 10 consultants, undergo 6 diagnostic tests, and receive treatment with PPI therapy and a trial of the UES assist device. In this research protocol, patients will present for 2 clinic visits, have diagnostic testing expedited and scheduled all within one setting, and undergo a streamlined therapeutic flow of PPI therapy, and UES assist device within 2 months. This study protocol was specifically designed to entail minimal perturbation to participants, including time and cost, and provide a streamlined and efficient evaluation.

## SPECIFIC AIMS & DATA ANALYSIS

**Aim 1:** To determine the ability of novel diagnostic tools to predict symptom-based treatment response in suspected RALS.

### ***Data Analysis for Aim 1***

Aim 1 analysis will employ a series of receiver operating characteristic (ROC) curves to assess and compare baseline diagnostic tool ability to predict patient-reported symptom response to treatment (positive or negative) at time points B (post-PPI) and C (post-UESAD+PPI). The areas under the ROC curves (AUCs) will be

***Sample Size & Power Calculation:*** At UCSD we plan to enroll 100 participants with an expected <15% dropout, with an overall analytic sample size of  $\geq 80$ . Assuming a minimal response rate of 50% to PPI and 67% to UESAD+PPI, a sample size of 80 and alpha level of 0.05 allows for 90% power to detect an AUC  $\geq 0.70$ . The UESAD+PPI response rate is an extrapolated combined estimate of UESAD alone and PPI alone from our prior data.

**Aim 2:** To examine the therapeutic efficacy of UES augmentation in suspected RALS.

## 10. HUMAN PARTICIPANTS

**Total number of participants to be enrolled at:** UCSD (100), University of Colorado Aurora CO (100). The study has already been active at CU since 2018 and actively enrolling as described in the progress report.

**A. Inclusion:** Age 18-89 years male and female, >8 weeks of symptoms of sore throat, throat clearing, and/or voice hoarseness, naïve to PPI or able to stop for 8 weeks, any ethnic background

**B. Exclusion criteria:** Laryngeal mass lesion on laryngoscopy (if performed); Pregnant; Breastfeeding; Unable to consent in English or Spanish as questionnaires are only validated in English and Spanish; Imprisoned; PPI intolerance; Contraindication to UESAD use per manufacturer guidelines which include:

- Patients with implants or implant parts that reside in the area where UESAD is applied.
- Patients with an implanted pacemaker, implanted cardioverter defibrillator (ICD), vagus nerve stimulator, or other such similar devices implanted in the neck.
- Patients diagnosed with glaucoma.
- Patients who had a malignancy of the neck, including neck surgery.
- Patients that may have an altered mental status including due to the use of sedative drugs or narcotics.
- Patients with carotid artery disease, thyroid disease, a history of cerebrovascular disease, or any disorder of connective tissues (e.g., Marfan's Syndrome or Ehlers-Danlos Syndrome).
- Patients who use nocturnal NIV machines such as CPAP or BiPAP.

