#### **19. EXPENSE TO PARTICIPANT**

The study protocol is designed so that participants will not incur any expenses outside of standard of care, and so that participants will receive compensation for participation.

The following procedures are standard of care for this patient population at UCSD and the procedure and related side effects will be covered by insurance: esophageal manometry, pH impedance, and PPI therapy.

Questionnaires are standard of care for this patient population at UCSD and there are no costs related to questionnaires.

Salivary peptest is not standard of care, and the costs (equipment and processing) will be covered by the PI as a research expense.

The UES assist device is standard of care, and typically obtained over the counter (\$199) by the patient. In this study the UES assist device will be covered by the PI as a research expense and provided to the participant free of cost.

	Standard of Care	Coverage	Visit Time (mins)	Costs to Manage Side Effects
Esophageal manometry	Yes	Insurance	45	Not anticipated, but would be covered as standard of care by Insurance
pH impedance	Yes	Insurance	45	Not anticipated, but would be covered as standard of care by Insurance
Questionnaires	Yes	No coverage needed	10	None
Salivary peptest	No	Research costs	2	None
4 week PPI therapy	Yes	Insurance	Not applicable	Covered as standard of care by Insurance
UES Assist Device	Yes	Typically self-pay; In this study will be a research cost	30 min visit to receive device	Not anticipated, but would be covered as standard of care by insurance

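### Eligibility controls earlier PPI use but not current use of the UES assist device, and no visible text bars or records band use before Visit 4, so the B-to-C device contrast can be diluted

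*Combined protocol and SAP*

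**What the plan says.** Section 10 (Human Participants), inclusion, requires patients to be "naïve to PPI or able to stop for 8 weeks, any ethnic background". The device appears in the exclusion list only through safety: "Contraindication to UESAD use per manufacturer guidelines which include", followed by items such as neck implants, glaucoma and carotid disease. Current or past use of the band is not mentioned.

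Elsewhere the protocol describes a device that patients can readily have. Section 19 states: "The UES assist device is standard of care, and typically obtained over the counter", at $199. Section 9, under the Mid-Treatment Visit, says it is "available over the counter for this proposed participant population, and is not considered a research intervention". The closing paragraph of the Study Protocol part of Section 9 says that patients with suspected RALS typically "receive treatment with PPI therapy and a trial of the UES assist device".

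The study itself supplies the band at Visit 4, after four weeks of PPI. Section 9 describes the week 2 and week 3 calls as covering PPI use, adherence and a visit reminder. They follow an attached script that is not part of the text.

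The Aim 2 hypothesis in Section 6 is that "UESAD in adjunct to PPI will result in greater symptom response versus PPI alone". The design is single-arm and non-controlled. The Aim 2 analysis compares the change from A (baseline) to B (post-PPI) with the change from B to C (post-UESAD+PPI).

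**The concern.** With no control arm, each participant's own PPI-only period is the only comparator for the device. The comparison works only if the device is absent until Visit 4 and present afterwards. The plan protects the PPI side with a naive-or-stop rule and leaves the device side open.

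Two groups matter, and they act differently:

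- **Using the band from before baseline.** The device is present at A, B and C. The A-to-B change still reflects adding PPI, on top of the device. The B-to-C change contains no device introduction.
- **Starting the band in weeks 0 to 4.** Device benefit falls into A-to-B, where it is read as PPI effect, and is missing from B-to-C.

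Both pull the B-to-C contrast towards no added benefit. In both, the response recorded at B for the Aim 1 ROC analysis as a response to PPI is in fact a response under PPI plus device. If band use is never recorded, a null B-to-C result could mean that the device adds nothing or that some participants already had it, and the data could not separate the two.

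**Working it through.** **Text check.** Following the written criteria for a patient who wears the band at screening:

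1. Inclusion (Section 10) covers age, more than 8 weeks of symptoms and the PPI condition. Band use is not addressed.
2. Exclusion (Section 10) lists device contraindications only. Band use is not addressed.
3. Screening (Section 11) covers current medications, diagnosis, and gastroenterology and laryngology records. Device use is not named, and an over-the-counter purchase need not appear in any of them.
4. Weeks 0 to 4 (Section 9) have calls on PPI use and adherence. No device question is stated.
5. Section 14 monitors device compliance by telephone, but does not tie this to weeks 0 to 4.

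The patient is eligible, and no described step records the exposure.

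**The plan's own power figure.** Inputs from the Aim 2 sample size paragraph (Section 9): n = 80, correlation between repeated measures at least 0.5 (0.5 used), effect 0.37 SD, power 90%. Alpha 0.05 is stated for Aim 1. It is assumed here for Aim 2, two-sided.

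- SD of the change = SD × √(2 × (1 − 0.5)) = 1.0 SD.
- Noncentrality = 0.37 × √80 = 3.31.
- Power = 90.5% (noncentral t, 79 df), or 91.1% by the normal approximation.

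The stated 90% reproduces.

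**Dilution.** Let f be the share of analysed participants already on the device at B, and assume that their B-to-C change is zero. The mean change becomes 0.37 × (1 − f). The documents give no value for f, so the range is an assumption.

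| f | Mean B-to-C change (SD) | Power, n = 80 | n for 90% power |
|---|---|---|---|
| 0% | 0.370 | 90.5% | 79 |
| 5% | 0.352 | 87.4% | 87 |
| 10% | 0.333 | 83.7% | 97 |
| 20% | 0.296 | 74.4% | 122 |

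Mixing users and non-users also adds f(1 − f) × 0.37² to the variance of the change. This lowers the three diluted powers only slightly, to 87.2%, 83.3% and 73.5%.

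**Sensitivity to the other inputs.**

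- Correlation 0.6 instead of 0.5: SD of change = √(2 × 0.4) = 0.894. With n = 80, power is 95% at f = 0, 91% at f = 10% and 83% at f = 20%.
- Both sites pooled, taking about 160 analysed (an assumption: 80 at each site), correlation 0.5: power is 99.6% at f = 0 and 96% at f = 20%.

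Neither change removes the bias in the estimate. The mean B-to-C change is still multiplied by (1 − f).

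**The case against.** The strongest points on the other side, and what stands of each:

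- **Use might be detected.** The phone scripts are attached to the protocol but not visible. Section 15 mentions two-weekly calls that ask about problems with the device or treatment. Patients come from their own treating investigators' clinics, and staff fit the band in person at Visit 4. This stands: a reader might infer that early use would go undetected, but the text supports only that no described step records it. Even if a script asks, no eligibility or analysis rule says what to do with the answer.
- **Past users do not contaminate the PPI period.** This stands. A reader might infer that anyone who has ever tried the band spoils the comparison. Someone who tried it and stopped is off it at A and B and starts it at Visit 4 like everyone else. Such patients may differ in likely response or expectation, which is a question of case mix.
- **Both contrasts are wrong for every user.** This reading is too strong. For a patient on the band throughout, the device is constant from A to B, so that change still measures adding PPI.
- **Early purchase is unlikely.** The band costs $199 and is supplied free at Visit 4. This makes purchase in weeks 0 to 4 less likely, but does nothing about patients who already own one.
- **The usual-care statement describes a whole pathway.** This is fair. It does not say that patients arrive wearing the band. It makes prior exposure plausible without giving its frequency.
- **The power loss is close to a worst case.** Users may still change from B to C through longer PPI, new fitting and adherence calls. Correlation 0.5 is the plan's floor, and 80 is the UCSD sample only. This stands, and the figures are illustrative.

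**Conclusion.** The concern holds in a limited form. Section 10 controls exposure to one of the two study treatments and not the other, and no visible text bars or records band use before Visit 4. Followed as written, the protocol enrols current band users, who contribute no device introduction to the trial's only device contrast. Early starters shift device benefit into the PPI period. The bias runs towards no added effect of the device, against the trial's own hypothesis, and the post-PPI response label in Aim 1 is wrong for both groups.

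The size is unknown. The fall from 90% power to about 87%, 84% or 74% rests on assumed user shares of 5%, 10% and 20%, n = 80, correlation 0.5, a two-sided 0.05 test and no B-to-C change in users. Power is higher at each share if the correlation is higher or the sites are pooled. The plan's 90% figure is not itself wrong, and it applies as stated if no one uses the band before Visit 4. The point deserves a change because the comparator is single-arm, the remedy is small, and band use that is not recorded at the time may not be recoverable later.

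**What to change.** 1. In Section 10, add an eligibility condition on current UESAD use that mirrors the PPI one: not using it, or able to stop before baseline. Any interval is for the investigators to set. Past users who have stopped need not be excluded.
2. At consent, ask participants not to obtain a band before Visit 4.
3. Record prior and current band use at baseline, at the existing week 2 and week 3 calls, and at Visit 4. If the attached scripts already ask, say so in Section 9.
4. State in the Aim 2 analysis that the A-to-B and B-to-C comparisons will be repeated without anyone who reports use before Visit 4, including participants already enrolled at Colorado where this can be established. Mark the same people in the Aim 1 analysis of response at B.

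Cost: one eligibility line, one sentence at consent, one added question at existing contacts and one sensitivity analysis. A few current users may become ineligible.

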## 11. RECRUITMENT AND PROCEDURES PREPARATORY TO RESEARCH

**How will participants be identified for recruitment?** The research assistant (RA)/PI will screen eligible patients coming in for evaluation in the clinic, endoscopy unit and motility lab that are patients of study investigators. The RA/PI will notify study investigators/treating MDs if eligible participant meeting inclusion criteria is identified. RA will keep a password protected screening list stored in a secure server separate from research data. This will protect identifiers from improper use and disclosure. A partial HIPAA waiver will be used for the minimal risk record review because identifying and contacting thousands of potential subjects would not be feasible for a medical record review where results would not change care the individuals already would have received, and waiver will not adversely affect the rights of welfare of the subjects.

- 1. What PHI will be accessed to identify participants?** Participants name, DOB, MRN, current medications, disease diagnosis, and relevant medical records (gastroenterology and laryngology records) will be accessed to identify if a patient meets inclusion criteria. No PHI will be stored in the screening log if the patient does not meet the inclusion criteria. This will protect identifiers from improper use and disclosure.
- 2. When will participants be approached for recruitment?** If treating MD/study investigator approves, the RA will call the potential research participant using the pre-screening phone script to notify the participant about the study, review eligibility and answer any questions and/or will contact the potential research participant in person in clinic. They will be given the consent form

and sufficient time to read it and ask any questions they may have. They will be given the opportunity to speak to the PI about any questions they have that cannot be answered by the RA.

- 3. Who can refer patients to the study?** Patients may be referred to the study by study investigators, and are participant to the same screening process to determine if they are eligible. Patients will not be obtained from any recruitment database.
- 4. Who will not be considered for recruitment?** Participant must be able to consent to the study. This protocol involves minimal risk, and/or targets only populations wherein impaired decision-making capacity is unlikely. Based upon past experience, we expect that the population of patients we will be including in this protocol will be competent to give informed consent. If there is any concern by an investigator that a potential research participant has a condition or circumstance that is associated with a possible decrease in decision making capacity, that participant will not be included in the study.

At risk populations including but not limited to prisoners, pregnant women, breastfeeding women, the mentally disabled, cognitively impaired, those requiring legal adult representation, and individuals under the age of 18 will not be approached. Pregnant women are excluded from our protocols, to make that distinction clear, we will ask if the potential research participant is pregnant at when determining eligibility. Breastfeeding women are excluded from our protocols. To make that distinction clear, the we will ask about breastfeeding when determining eligibility.

If potential research participants are not interested in participating in the study then their identifying information in the screening log will be destroyed at the earliest opportunity consistent with conduct of research.

